3.3. Justification for Study Design and Selection of Population

The study population will be composed of female and male patients, aged 18 to 70 years, inclusive, with a diagnosis of migraine and MDD. Patients must have been diagnosed with migraine (as defined by the ICHD-3 criteria [IHS, 2013], see Appendix I) at least 12 months prior to the screening visit (V1). The diagnosis of migraine will be prospectively confirmed via a review of migraine data recorded daily during a 28-day baseline period in an electronic diary device. Patients must also have a history of MDD according to the DSM-V criteria at least 12 months prior to the screening visit (V1) and have active symptoms of depression as assessed

by a PHQ-9 score of at least 10 at the screening visit (V1). Investigators must document that patients had the diagnosis of migraine and MDD for at least 12 months prior to the screening visit (V1). MDD is a common comorbidity with migraine. Post hoc analyses of the HALO CM study indicated that depressive symptoms improved in migraine patients with baseline PHQ-9 of 10 to 19. This study is designed to further evaluate the efficacy of fremanezumab in this population.

Commercially approved dosing regimens will be investigated in the double-blind treatment phase. Both the monthly dose of 225 mg and quarterly dose of 675 mg, which will be used in the current study in the double-blind and the open-label periods, respectively, were equally efficacious in the pivotal trials. For treatment details, see Section 5.1.

One objective of this study is to determine whether migraine and depression are affected independently by fremanezumab or whether improvement in one disease precedes and may causally improve the other disease via their bidirectional association (see Section 1.1.2 for further background information). By assessing both migraine and depression symptoms at multiple time points and by having placebo patients cross over to active treatment, we will have more data points by which to make this assessment. Additionally, the open-label extension phase is intended to provide the placebo-treated patients the opportunity to receive potential benefit from therapeutic doses. It also provides an opportunity to further explore efficacy and tolerability in this patient population and to generate data on switching from the monthly to the quarterly dose.

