Adverse events and health care resource utilization inquiry ^l	X ^q	X	X	X	X		X
Dispensing of IMP		X	X	X	X		
Administration of IMP ^f		X	X	X	X		
Hypersensitivity/ anaphylaxis ⁵		X	X	X	X		X
Concomitant medication and therapy inquiry ^l	X	X	X	X	X		X

^a In the case of early termination, site personnel should perform a follow-up phone call to ensure the patient does not report suicidal ideation or behavior. Phone calls should be performed once weekly for 2 weeks. If signs of suicidality are identified during the follow-up phone call, the site personnel should provide direction to the patient for further psychiatric evaluation at the site or at a community psychiatrist referenced by the site. Relevant emergency psychiatric care services should be notified in the event that the patient is deemed to be a threat to themselves.

^b Patients will complete the screening visit not more than 28 (+3) days before the randomization visit (V2 [day 1]). All visit 2 procedures must be performed before study drug administration.

^c Patients will continue into the open-label extension phase at week 12 and will all receive a quarterly dose of 675 mg sc fremanezumab.

- ^d Collection of prior medications for migraine and/or depression is limited to those medications administered within the past 10 years or for any indication with the past 5 months before screening (V1).
- ^e In addition, inquire and record start/stop date of menstrual period for women of child-bearing potential only at each visit as part of physical examination assessments.
- ^f Height will be measured only at the screening visit (V1).
- ^g This assessment will be done predose. A single ECG will be performed. If results are abnormal, the ECG will be repeated 1 time.
- ^h Before pulse and blood pressure are measured, the patient must be in a supine or semi-erect/seated position and resting for at least 5 minutes. The same position and arm should be used each time vital signs are measured for a given patient.
- ⁱ For details see [Appendix E](#).
- ^j On dosing days, the test or questionnaire should be completed before study drug administration.
- ^k The FSH assessment applies only to women thought to be postmenopausal at the screening visit (V1). If the results show an elevated FSH (>35 U/L) and the patient has had no menses for at least 12 months, they do not need urine pregnancy testing.
- ^l This is a required procedure for unscheduled visits. See further details in [Appendix B](#).

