- g. The patient has a history of MDD according to the DSM-V criteria at least 12 months prior to the screening visit (V1). Patients may take a single medication prescribed for the treatment of depression as long as the dose of that medication has been stable for at least 8 weeks prior to the screening visit (V1) and expects to remain at the stable dose throughout the study ([Appendix G](#)).
- h. The patient has a PHQ-9 score of at least 10 at the screening visit (V1).
- i. The patient has a Mini Mental State Examination score of at least 26 points at the screening visit (V1).
- j. The patient is in good health in the opinion of the investigator as determined by medical evaluation, including medical and psychiatric history, physical examination, laboratory tests, and cardiac monitoring.
- k. The patient has a body weight ≥ 45 kg and a body mass index within the range of 17.5 to 34.9 kg/m², inclusive.
- l. [Revision 2] The patient demonstrated compliance with the electronic headache diary during the 28-day baseline period by entry of headache data on a minimum of 21 days cumulative during the 28-day baseline period (~75% diary compliance).
- m. Women may be included only if they have a negative serum beta-human chorionic gonadotropin (β -HCG) test at the screening visit (V1), are sterile or postmenopausal, and are not lactating (not applicable for patients participating in safety follow-up only). Definitions of sterile and postmenopausal are given in [Appendix E](#).
- n. Women of child-bearing potential whose male partners are potentially fertile (ie, no vasectomy) must use highly effective birth control methods for the duration of the study and for 6 months after discontinuation of IMP (for details see [Appendix E](#)).
- o. Men must be sterile or, if they are potentially fertile/reproductively competent (not congenitally sterile) and their female partners are of child-bearing potential, must use a condom for the duration of the study and for 6 months after discontinuation of IMP. For the purpose of this study, vasectomized men must use a condom if their partners are of child-bearing potential. Definitions of women of non-child-bearing potential, sterile and postmenopausal women; male contraception; and highly effective birth control methods, including examples, are given in [Appendix E](#).

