APPENDIX B. STUDY PROCEDURES AND ASSESSMENTS BY VISIT

1. Procedures for Screening (Visit 1, Days -28 to -1)

The screening visit (V1) will take place not more than 28 (+3) days before the randomization visit (visit 2). The following procedures will be performed at visit 1:

- obtain written informed consent before any study-related procedures are performed
- review inclusion and exclusion criteria
- review medical and psychiatric history
- record demographic characteristics
- review prior medications and treatment history
- perform full physical examination (including height and weight)
- perform 12-lead electrocardiogram (ECG)
- perform vital signs measurements
- perform safety laboratory assessments
- perform serum beta-human chorionic gonadotropin (β -HCG) pregnancy test (for women of child-bearing potential and women thought to be postmenopausal) at the screening visit (V1) and follicle-stimulating hormone test (for women thought to be postmenopausal)
- inform patients of study restrictions and compliance requirements
- complete Mini Mental State Examination
- complete Patient Health Questionnaire-9 (PHQ-9)
- complete the eC-SSRS Lifetime version (used in conjunction with qualified clinician's clinical judgment to assess the patient's suicidal ideation [severity and intensity] and behavior)
- provide electronic headache diary
- complete electronic headache diary entries
- perform adverse events and health care resource utilization inquiry
- perform concomitant medication and therapy inquiry

**2. Procedures Before Administration of Investigational Medicinal Product(s)
(Randomization [Visit 2, Day 1 +3 days]) (Double-Blind Treatment Phase)**

Patients who meet the inclusion and exclusion criteria at visit 1 will continue to visit 2, when baseline assessments will be conducted.

The following procedures will be performed at visit 2:

- review inclusion and exclusion criteria
- assign randomization/treatment numbers and enter in the electronic case report form (eCRF)
- perform physical examination
- perform 12-lead ECG
- perform vital signs measurement
- perform safety laboratory assessments
- perform urine β -HCG pregnancy test (for women of child-bearing potential)
- review study compliance
- complete the eC-SSRS Since Last Visit version (used in conjunction with qualified clinician's clinical judgment to assess the patient's suicidal ideation [severity and intensity] and behavior)

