- complete Hamilton Depression Rating Scale-17 items (HAM-D 17) (qualified staff member to administer and record)
- complete Hamilton Anxiety Scale (HAM-A) (qualified staff member to administer and record)
- complete 6-item Headache Impact Test (HIT-6)
- complete Clinical Global Impression-Severity (CGI-S)
- complete Migraine-Specific Quality of Life (MSQoL)
- complete Work Productivity and Activity Impairment Questionnaire General Health (WPAI-GH)
- complete electronic headache diary
- review electronic headache diary
- perform adverse events and health care resource utilization inquiry
- dispense investigational medicinal product (IMP)
- patient self-administration of IMP
- assess for hypersensitivity/anaphylaxis
- perform concomitant medication and therapy inquiry

3. Procedures During Administration of Investigational Medicinal Product (Visit 3, Day 29 ±3 days) (Double-Blind Treatment Phase)

The following procedures/assessments will be performed at visit 3:

- perform physical examination
- perform 12-lead ECG
- perform vital signs measurement
- perform safety laboratory assessments
- perform urine β -HCG pregnancy test (for women of child-bearing potential)
- review study compliance
- complete PHQ-9
- complete the eC-SSRS Since Last Visit version (used in conjunction with qualified clinician's clinical judgment to assess the patient's suicidal ideation [severity and intensity] and behavior)
- complete HAM-D 17 (qualified staff member to administer and record)
- complete HAM-A (qualified staff member to administer and record)
- complete HIT-6
- complete CGI-S
- complete MSQoL
- complete WPAI-GH
- complete electronic headache diary
- review electronic headache diary
- perform adverse events and health care resource utilization inquiry
- dispense IMP
- patient self-administration of IMP
- assess for hypersensitivity/anaphylaxis
- perform concomitant medication and therapy inquiry

4. Procedures During Administration of Investigational Medicinal Product (Visit 4, Day 57 ±3 days) (Double-Blind Treatment Phase)

The following procedures/assessments will be performed at visit 4:

- perform physical examination
- perform 12-lead ECG
- perform vital signs measurement

- perform safety laboratory assessments
- perform urine β -HCG pregnancy test (for women of child-bearing potential)
- review study compliance
- complete PHQ-9

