### 4.2. Specification of Baseline Values

For migraine days, the baseline value is the total number of migraine days during the 28-day baseline period. If the baseline period is greater or less than 28 days, the baseline value will be normalized to 28 days. In addition, if the baseline period is 28 days but there are days with missing diary, the baseline value will be normalized to 28 days.

For all other assessments, the baseline value is the last observed data prior to the first dose of study drug.

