**6.4.4. Other Analysis**

Correlation between the change from baseline in the PHQ-9 total score and the change from baseline in the monthly average number of migraine days will be presented with all visits combined through the 24-week period after the first dose of study drug. All visits will be combined and both treatments will be combined in the analysis. The open-label mITT analysis set will be used for the analysis. A scatter plot will also be presented.

To assess whether improvements in headaches precede changes in depression, a graph of mean change from baseline in monthly number of migraine days versus mean change from baseline in PHQ-9 total score during the 6-month treatment period will be presented by month and double-blind treatment group. The open-label mITT analysis set will be used for the graph.

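### PHQ-9 is not measured at day 1, so the graph of whether headache improves before depression counts about four untreated weeks, and regression to the mean, as early improvement in depression

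*SAP*

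**What the plan says.** - **The question.** Protocol 3.3: "One objective of this study is to determine whether migraine and depression are affected independently by fremanezumab or whether improvement in one disease precedes". The sentence goes on to raise a causal effect of one condition on the other.
- **The analysis.** SAP 6.4.4 answers it with a graph: "To assess whether improvements in headaches precede changes in depression, a graph of mean change from baseline in monthly number of migraine days" against mean change in PHQ-9 total score over six months, by month and double-blind arm, in the open-label mITT set. The same section plans a correlation of the two changes with all visits and both arms pooled.
- **The baseline rule.** SAP 4.2 takes the 28-day run-in as the migraine-day baseline. For everything else: "For all other assessments, the baseline value is the last observed data prior to the first dose of study drug".
- **The PHQ-9 schedule.** Protocol Table 4 marks PHQ-9 at V1, V3, V4, V5 and V6, and the V2 cell is empty. Appendix B agrees. It says patients "will continue to visit 2, when baseline assessments will be conducted", but its visit 2 list has HAM-D 17, HAM-A, HIT-6, CGI-S, MSQoL, WPAI and eC-SSRS and no PHQ-9. The entry "complete PHQ-9" returns at visit 3 (day 29).
- **The entry threshold.** Inclusion criterion h: "The patient has a PHQ-9 score of at least 10 at the screening visit (V1". Nothing requires this again at day 1.
- **The gap.** Table 4, note b: "Patients will complete the screening visit not more than 28 (+3) days before the randomization visit".

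**The concern.** A question about which condition improves first needs both curves to start from the same moment. Here they do not. The migraine baseline ends when dosing starts; the PHQ-9 baseline was taken about four weeks before. Whatever happens to PHQ-9 during the untreated run-in is plotted as part of the first change on treatment.

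The screening PHQ-9 is also the score that patients were selected on. A group chosen for scoring at or above a cut-off is expected to score lower when measured again, with no treatment and no true change. This pushes the PHQ-9 curve down at its first plotted point in both arms. Read within an arm, the graph is tilted towards depression appearing to improve early relative to migraine. Neither document mentions the different starting points.

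**Working it through.** The plan gives no figure for this, so there is none to reproduce. The check has a timing part, which needs no assumptions, and a size part, which does.

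**1. Timing, from Table 4 and SAP 4.2.** There is no day 0.
- Screening to first dose: day -28 to day -1 = 28 days, or up to 28 + 3 = 31.
- First dose to first post-dose PHQ-9: day 1 to day 29 = 28 days (window ±3).
- First PHQ-9 change interval: 28 + 28 = 56 days, of which 28/56 = 50% is before any dose. With a 31-day gap it is 31/59 = 53%.
- Migraine days: the baseline window ends at day -1, so no untreated gap separates it from month 1.

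Recall widens the difference. PHQ-9 asks about the past two weeks (protocol 6.1.3), so a score at day -28 describes roughly days -42 to -28, before the migraine baseline window opens.

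**2. Regression to the mean in PHQ-9.** The mean, SD and four-week retest correlation r are not in the documents and are assumed. For a normal score selected at 10 or more (cut at 9.5 for continuity), with no true change:

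expected fall = (1 − r) × SD × φ(a) / (1 − Φ(a)), where a = (9.5 − mean)/SD.

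Worked case, mean 10, SD 5, r = 0.7: a = −0.1; φ(a)/(1 − Φ(a)) = 0.397/0.540 = 0.735; fall = 0.3 × 5 × 0.735 = 1.10 points.

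| Mean before selection | SD | r | Expected fall (points) |
|---|---|---|---|
| 8 | 6 | 0.6 | 2.31 |
| 10 | 5 | 0.6 | 1.47 |
| 10 | 5 | 0.8 | 0.74 |
| 10 | 5 | 0.9 | 0.37 |
| 12 | 5 | 0.85 | 0.38 |
| 14 | 4 | 0.9 | 0.10 |

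Over the full grid (mean 8, 10, 12, 14; SD 4, 5, 6; r 0.6, 0.7, 0.8, 0.85, 0.9) the range is 0.10 to 2.31 and the median 0.6. True change in the run-in comes on top.

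**3. The same calculation for migraine days.** At least 4 migraine days are required in the same 28 days that form the baseline (protocol 4.1, criterion e), so this curve is not free of selection either. With the cut at 3.5 and assumed mean 8, 10 or 14, SD 5 or 6, r 0.6 or 0.8, the expected fall is 0.04 to 0.93 days. Regression to the mean therefore enters both curves; the untreated four-week gap is specific to PHQ-9.

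**4. Scale.** Protocol 1.1.3 cites within-arm PHQ-9 falls of 9.5 to 10.5 points over 12 weeks on fremanezumab, in patients with baseline scores of 10 to 19. Against 9.5, the median artefact is 0.6/9.5 = 6% and the largest 2.31/9.5 = 24%. That group was itself defined by its baseline score, so the cited falls may contain the same effect.

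**5. The correlation.** Subtracting the same constant from every patient's PHQ-9 change leaves a correlation unchanged. Only differences between patients in run-in change can affect it, as noise. Their size cannot be judged from the documents.

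**6. After the change.** With a day-1 PHQ-9 baseline the untreated part of the first interval falls from about 28 days to 0. Under the model in step 2, with equal retest correlation across visits, the expected artefact falls to about 0, because selection was on the screening value.

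**The case against.** The graph is split by randomised arm. Drift and regression to the mean should be about equal in both, so the placebo curve shows their size to week 12, and a reader who compares arms is not misled. Under a single retest correlation the offset is also the same at every later visit: it lowers the level of the curve and leaves its shape from month 1 onward alone. Both points stand. They limit the harm but do not remove it. SAP 6.4.4 does not ask for a placebo-adjusted reading, there is no placebo arm after week 12, and an ordering question is read mainly from the first points.

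PHQ-9 is a defensible choice of scale. The HAM-D 17 form in SAP Appendix C names headaches in items 11 (somatic anxiety) and 13 (general somatic symptoms); PHQ-9 has no headache item. Fewer headaches could lower HAM-D 17 directly and make the two conditions seem to move together. This stands, and is why HAM-D 17 should be added and not substituted.

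Day-1-anchored results are already planned: HAM-D 17 change at weeks 4, 8 and 12 (SAP 6.3.1.2) and migraine days by month (SAP 6.2.3.1). That is correct, but they are not brought together for the timing question.

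Finally, the analysis is descriptive, carries no test and sits under other analyses. The word objective appears in the design rationale and not in the visible objectives table; the exploratory objectives are redacted, so their wording cannot be checked. This bears on priority, not on whether the point is right.

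**Conclusion.** The point holds for the within-arm timing reading of the SAP 6.4.4 graph. That about half of the first PHQ-9 change interval precedes any dose follows from the schedule and the baseline rule alone. Selection on the screening score gives the expected direction, a fall. The size cannot be fixed from the documents: regression to the mean alone is about 0.1 to 2.3 PHQ-9 points on assumed inputs, and true run-in change, in either direction, is unknown.

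A reader might infer more, and the documents do not support it:
- that the graph will show depression improving first whatever the drug does. The arms are shown separately, and migraine days carry some regression to the mean too;
- that the PHQ-9 treatment comparison is biased. Both arms share the screening baseline, so the between-arm difference is not biased by the gap;
- that the key secondary endpoint is affected. HAM-D 17 is measured at day 1 and has no entry threshold;
- that the pooled correlation is shifted. A common offset does not move it.

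This is worth correcting because the protocol states the order of improvement as an aim and most of the remedy uses data already collected. It does not touch the confirmatory results.

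**What to change.** 1. **SAP 6.4.4.** Add a parallel graph and correlation using HAM-D 17 change from day 1, collected at V2 to V6. Show them with the full score and with items 11 and 13 left out. Keep the PHQ-9 graph, state on it that its baseline is the screening value, and show next to it the placebo-adjusted PHQ-9 change to week 12. The model in SAP 6.4.1.2 already yields that difference at weeks 4, 8 and 12. Cost: SAP wording and a little extra analysis, with no new data.
2. **If patients are still being randomised.** Add PHQ-9 before dosing at V2, where the other scales are already completed, and use it as the baseline for the timing analysis in patients who have it. State explicitly that screening and day-1 baselines are not mixed, because the last-value rule in SAP 4.2 would otherwise mix them. Keep the V1 score for eligibility and stratification. Cost: a minor protocol amendment and one short questionnaire; patients enrolled earlier will lack the day-1 score.

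If enrolment is closed, item 1 alone gives a depression curve that starts at the first dose, and shows how far the PHQ-9 curve can be read.

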## 7. MULTIPLE COMPARISONS AND MULTIPLICITY

A fixed-sequence (hierarchical) testing procedure will be implemented to control the type 1 error rate at 0.05. The primary endpoint will be tested first at a type I error rate of 5%. If the analysis is statistically significant (p-value <0.05), then the key secondary hypothesis will be tested. If not statistically significant, confirmatory hypothesis testing will not be carried out on the remaining hypotheses. This process will repeat accordingly to the order of the secondary endpoints as specified in section 6.3. [REDACTED]

[REDACTED]

[REDACTED]

## **8. SAFETY ANALYSIS**

### **8.1. General**

The safety analysis sets will be used for all safety analyses. Summaries will be presented separately for the double-blind treatment period and open-label treatment period. For the double-blind treatment period, summaries will be presented by treatment group, unless otherwise stated. For the open-label treatment period, summaries will be presented by double-blind treatment group and all patients (ie, total).

### **8.2. Duration of Exposure to Study Drug**

Duration of treatment (days treated) for the double-blind treatment period is the number of days on treatment started from the 1st study drug administration day to the week 12 or double-blind early withdrawal visit day (week 12 or double-blind early withdrawal visit day – first day of study drug + 1). For patients who are lost to follow-up during the double-blind treatment period, the EOT visit date is defined as the last study drug administration + 27.

Duration of treatment (days treated) for the open-label treatment period is the number of days on treatment started from the 1st study drug administration day in the open-label treatment period to the week 24 or open-label early withdrawal visit day (week 24 or open-label early withdrawal visit day – first day of study drug in the open-label treatment period + 1). For patients who are lost to follow-up during the open-label treatment period, the EOT visit date is defined as the last study drug administration + 27.

Number (%) of patients receiving 1 dose, 2 doses, and 3 doses during the double-blind treatment period will be summarized using descriptive statistics. Duration of treatment (days) during the double-blind and open-label periods will also be summarized using descriptive statistics.

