7.1.2. Recording and Reporting of Adverse Events

For recording of adverse event, the study period is defined for each patient as the time period from signature of the ICF to the end of the follow-up period. The follow-up period of recording of adverse events is defined as 12 weeks after the last dose of IMP. The period for reporting treatment-emergent adverse events is defined as the period after the first dose of IMP is administered and until end of follow-up period on day 169 (± 3 days).

All adverse events that occur during the defined study period must be recorded on both the source documentation and the eCRF, regardless of the severity of the event or judged relationship to the IMP. For serious adverse events, the serious adverse event form must be completed and the serious adverse event must be reported immediately (Section 7.1.5.3.1). The investigator does not need to actively monitor patients for adverse events after the defined period. Serious adverse events and adverse events of special interest occurring in a patient after the defined study period should be reported to the sponsor if the investigator becomes aware of them, following the procedures described in Section 7.1.5.3.1.

At each contact with the patient, the investigator or designee must question the patient about adverse events by asking an open-ended question such as "Have you had any unusual symptoms or medical problems since the last visit? If yes, please describe." All reported or observed signs and symptoms will be recorded individually, except when considered manifestations of a medical condition or disease state. A precise diagnosis will be recorded whenever possible. When such a diagnosis is made, all related signs, symptoms, and any test findings will be recorded collectively as a single diagnosis on the eCRF and, if it is a serious adverse event, on the serious adverse event form.

The clinical course of each adverse event will be monitored at suitable intervals until resolved, stabilized, or returned to baseline; or until the patient is referred for continued care to a health care professional; or until a determination of a cause unrelated to the IMP or study procedure is made.

The onset and end dates, duration (in case of adverse event duration of less than 24 hours), action taken regarding IMP, treatment administered, and outcome for each adverse event must be recorded on both the source documentation and the eCRF.

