## 2. STUDY DESIGN

### 2.1. General Design

This is an approximately 28-week, multicenter, randomized, double-blind, placebo investigational medicinal product (IMP)-controlled, parallel-group study to evaluate the efficacy and safety of fremanezumab self-administered at monthly doses of 225 mg sc and a quarterly dose of 675 mg sc (ie, one dose using 3 prefilled syringes with 225 mg each) in adult patients with migraine and MDD. The study will consist of a 28-day (ie, 4-week) baseline period, a 12-week double-blind treatment phase followed by a 12-week open-label extension phase, and an end-of-treatment visit (approximately 12 weeks after the final dose of study drug).

The total duration of patient participation in the study is planned to be approximately 28 weeks. Patients are expected to complete the entire duration of the study.

Patients who fulfill the criteria for migraine will be further delineated as patients with chronic migraine (CM) or episodic migraine (EM), for stratification and other analyses.

CM is defined as:

Patient fulfills the following criteria for CM in prospectively collected baseline information during the 28-day baseline period:

- headache occurring on  $\geq 15$  days
- on  $\geq 8$  days, fulfilling any 1 of the following:
  - ICHD-3 diagnostic criteria C and D for 1.1 Migraine without aura (Appendix I of the study protocol)
  - ICHD-3 criteria B and C for 1.2 Migraine with aura (Appendix I of the study protocol)
  - probable migraine (a migraine subtype where only 1 migraine criterion is missing)
  - triptan or ergot derivative used to treat established headache.

EM is defined as:

The patient fulfills the following criteria for EM in prospectively collected baseline information during the 28-day baseline period:

- headache occurring  $\geq 4$  days but  $< 15$
- on  $\geq 4$  days, fulfilling any 1 of the following:
  - ICHD-3 diagnostic criteria C and D for 1.1 Migraine without aura (Appendix I of the study protocol)
  - ICHD-3 criteria B and C for 1.2 Migraine with aura (Appendix I of the study protocol)

- probable migraine (a migraine subtype where only 1 migraine criterion is missing)
- triptan or ergot derivative used to treat an established headache

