At the randomization visit (day 1), patients will be randomly assigned to 1 of 2 treatment groups of 225 mg sc fremanezumab or placebo in a 1:1 ratio. Patients will receive their assigned study treatment on visit 2 (day 1), visit 3 (day 29), and visit 4 (day 57) and then continue into the open-label extension phase in which all patients will receive a quarterly dose of 675 mg sc fremanezumab on visit 5 (day 85). Investigators can contact patients in between study visits per their clinical judgment.

Patients who complete all scheduled visits will have procedures and assessments performed at visit 6 (end of treatment [EOT]). Patients who withdraw from the study before completing the 24-week treatment phase will have visit 6 (EOT) procedures and assessments performed at their final visit. The end of study is defined as the last visit (end-of-treatment/early withdrawal visit [visit 6]) of the last patient.

Study procedures and assessments with their timing are summarized in Table 4 of the study protocol.

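### The SAP's last-dose + 27 end date for open-label patients lost to follow-up credits 28 days after a quarterly dose; the rule it applies to the monthly doses would credit 84

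*SAP*

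**What the plan says.** SAP section 8.2 defines duration of treatment separately for the two periods. Open-label days run to the actual end visit: "week 24 or open-label early withdrawal visit day – first day of study drug in the open-label treatment period + 1". When a patient is lost and there is no end visit, an end date is imputed. For the double-blind period the rule covers patients "lost to follow-up during the double-blind treatment period, the EOT visit date is defined as the last study drug administration + 27". For the open-label period it is identical: "lost to follow-up during the open-label treatment period, the EOT visit date is defined as the last study drug administration + 27".

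The dosing schedules of the two periods differ. SAP section 2.1 has double-blind doses on days 1, 29 and 57 and one quarterly open-label dose on day 85. It describes "a 12-week double-blind treatment phase followed by a 12-week open-label extension phase", with the end-of-treatment visit about 12 weeks after the final dose. Protocol section 7.1.2 uses the same horizon for safety: "The follow-up period of recording of adverse events is defined as 12 weeks after the last dose of IMP".

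**The concern.** The + 27 matches a 28-day dosing interval and looks carried over from the double-blind paragraph without adjustment. Nothing in either document gives a reason for crediting 28 days after a quarterly dose.

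It also sits badly with other definitions. SAP section 4.4 runs the treatment phase to visit 6 (day 169) or the end-of-treatment visit, and starts month 6 at 57 days after the fourth dose. A patient lost during month 6 could therefore have treatment-phase diary data dated after the treatment end that section 8.2 assigns. Likewise, Protocol section 7.1.2 counts adverse events as treatment-emergent until day 169 (±3 days), so an event on day 130 in a lost patient would be treatment-emergent yet lie outside that patient's recorded duration.

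At stake is a table that the SAP commits to produce: open-label duration of treatment, shown by double-blind group and in total. Protocol Table 4 schedules no visit between day 85 and day 169, so a lost patient will usually be one who never returns for visit 6. All such patients would be placed at exactly 28 days, which pulls down the minimum and mean and widens the SD.

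**Working it through.** **Inputs.** Doses on days 1, 29, 57 and 85, and a 12-week (84-day) open-label phase (SAP 2.1); visit 6 on day 169 ±3 (Protocol Table 4); end date = last dose + 27 (SAP 8.2); duration = end day - first dose day of the period + 1 (SAP 8.2).

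**Double-blind period, rule as written.** The intervals are 29 - 1 = 28, 57 - 29 = 28 and 85 - 57 = 28 days.
- Lost after dose 1: 1 + 27 - 1 + 1 = 28 days
- Lost after dose 2: 29 + 27 - 1 + 1 = 56 days
- Lost after dose 3: 57 + 27 - 1 + 1 = 84 days

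Each dose is credited with one full interval, so + 27 is the interval minus 1.

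**Open-label period, rule as written.** End day 85 + 27 = 112. Duration 112 - 85 + 1 = 28 days.

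**Open-label period, interval minus 1.** The interval is 169 - 85 = 84 days, so the offset is 83. End day 85 + 83 = 168. Duration 168 - 85 + 1 = 84 days.

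**Gap.** 84 - 28 = 56 days, and 56/84 = 67% of the interval. A nominal completer has 169 - 85 + 1 = 85 days (82 to 88 with the visit 6 window), which is 57 days more than a lost patient (54 to 60).

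**Effect on the mean.** The documents give neither the number entering the open-label phase nor the number lost in it. As an assumption, take 288 (the planned number of completers) as a rough size for that phase:

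| Assumed lost | Patients | Person-days (× 56) | Shift in mean (÷ 288) | Share of 288 × 84 = 24,192 days |
|---|---|---|---|---|
| 1% | 3 | 168 | 0.6 day | 0.7% |
| 5% | 14 | 784 | 2.7 days | 3.2% |
| 15% | 43 | 2,408 | 8.4 days | 10.0% |

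The 15% row treats the whole planned drop-out rate as open-label loss to follow-up and is an upper bound. Using all 340 randomized patients instead of 288 gives 0.5 day at 1% (3 × 56/340) and 2.8 days at 5% (17 × 56/340), so the choice of base hardly matters.

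**The case against.** The strongest reply is that section 8.2 measures time to a visit, not pharmacological coverage. A patient who attends an early withdrawal visit 30 days after the open-label dose is credited 31 days, although the same quarterly dose was given. A full dosing interval is therefore not the standard for other early leavers, and the SAP nowhere states interval minus 1 as a principle; it is inferred from how + 27 works in the double-blind period. This stands as a limit on the claim: the 56 days is a gap between two applications of one rule, not time that any patient was observed and not credited. It does not explain why a loss after three monthly doses earns 84 days and a loss after one quarterly dose of the same total amount earns 28.

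The second objection is that + 83 has its own bias: a patient who vanishes the day after dosing would get 84 days against 85 for a completer. That is true, but + 27 after a monthly dose has the same feature on a smaller scale. It can be handled with a cap.

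A reader might infer that open-label safety rates are distorted because exposure is their denominator. The documents do not support that. SAP section 8.3 counts each patient once per system organ class and preferred term, laboratory and vital-sign summaries are by visit or by patient incidence, and section 8 plans no exposure-adjusted rate. Nor does the SAP mix 28-day and 84-day conventions in one table: it contains no 84-day imputation rule, and the two periods are summarized separately.

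Finally, 288 is a planned number of completers, who by definition are not lost. It serves here only as an order of magnitude.

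**Conclusion.** The point holds, and it is minor. The open-label rule assigns 28 days where the convention the SAP follows for monthly dosing would assign 84, and neither document justifies the difference. It applies only to patients lost to follow-up in the open-label period; completers and patients with an early withdrawal visit are counted to their actual dates. It should not be read as every open-label patient losing 56 days.

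The consequence is confined to the descriptive summary of open-label duration. The shift of about 0.6 to 2.7 days in the mean rests on an assumed 1-5% loss among about 288 patients. Efficacy results, sample size and adverse event incidence do not use this quantity.

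**What to change.** In SAP section 8.2, define the open-label end date for patients lost to follow-up as last study drug administration + 83, and leave + 27 for the double-blind period. If crediting nearly a completer's duration to someone lost soon after dosing is unwanted, cap the date at the last diary entry or last contact; the diary is completed daily through the end-of-treatment visit, so a date will usually be available. If 28 days is in fact intended, the SAP should say why.

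The cost is one line of text and one derivation. No new data are needed, all analyses follow the final database lock (SAP section 2.5.2), and no dose, schedule or clinical rule is touched.
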